### 7.3 Specialty Assessments

**As of Amendment 5:** Due to the Sponsor's decision to discontinue the trial (effective 20Dec2018), only clinical safety-related evaluations will be conducted. Of the Specialty Assessments detailed below, ADA and samples for exploratory PK and PD assessments (in peripheral blood, skin biopsies, and tumor biopsies) will not be collected. Genomic samples for eligibility assessment were obtained at prescreening and analyzed; however post-dosing genomic samples will not be collected.

Note: Samples for ADA and samples for exploratory PK and PD assessments, if collected prior to implementation of this amendment, will not be analyzed and will be destroyed.

**The pre-Amendment 5 specialty assessments were as follows:**

Laboratory analyses detailed below will be performed at centralized Specialty Laboratory facilities. A detailed laboratory manual specifying sample collection, handling, storage, and shipment will be provided to the trial sites; retention time for specimens will be specified therein. Blood samples, skin biopsies, and tumor biopsies will be taken according to the schedule shown ([Table 5](#); [Appendix 10](#)).

Every effort will be made to collect samples at the timepoints specified. All analyses will be related to and used only with the data collected in the present trial or other Sym004-related trials, and the identity of the patient will remain confidential. The analyses will not have any medical consequences for the patient or their relatives.

**Table 5: Timepoints for Specialty Assessments (Arm A, Arm B, and Arm C)**

Sample Time	Cycle 1					Cycle 2			C Thereafter		EOT	1M FUP
	D1	D4 ±24h	D8	D15	D22	D1	D22	D25 ±24h	D1	D15		
ADA (peripheral blood)												
Prior to SOI	X			X		X			Odd # C			
Visit Day											X	X
PK (peripheral blood)												
Prior to SOI	X		X	X	X	X	X		X	X		
EOI (± 10m)	X		X	X	X	X	X		X	X		
6h > EOI (± 1h)	X						X					
24h > EOI (± 8h)	D2						D23					
Visit Day		X						X			X	X
Genomic Analysis (peripheral blood)												
Visit Day	prescreen*							X**			X***	
Pharmacodynamic Analyses (after confirmation of eligibility)												
Peripheral blood	screening/ pre-C1D1							X**,^			X***	
Skin biopsy	screening/ pre-C1D1					EOC1^		X**,^				
Tumor biopsy	screening/ pre-C1D1							X**,^				

Abbreviations (in alphabetical order): ADA, anti-drug antibody; C, cycle(s); D, day; EOI, end of infusion; EOT, end of treatment; h, hour; m, minutes; 1M FUP, 1-month follow-up; SOI, start of infusion

\*required at prescreening for eligibility

\*\*preferred day of sampling; coincides with “prior to crossover” for patients in Arm B and Arm C

\*\*\*EOT with Sym004; need not be repeated if patient is discontinuing at the EOC2

^ End of Cycle assessment may be conducted at any time during the week prior to Day 1 of the next cycle, including on Day 1 of the next cycle prior to dosing

**As of Amendment 5:** All specialty assessments have been omitted (effective 20Dec2018) with the exception of prescreening genomic sampling for eligibility assessment (\*).

### 7.3.1 Immunogenicity Assessment (Specialty Laboratory)

**As of Amendment 5:** Immunogenicity assessments have been omitted. Immunogenicity assessments were initially planned as follows:

*(To assess for formation of ADA; serum to be isolated)*

*(All samples must be taken prior to the IMP infusion of that visit. If a collected serum sample is inadequate or insufficient for ADA analysis, analysis may be done using serum from a PK sample from the same timepoint, if available)*

- Cycle 1
  - Day 1 (prior to dosing)
  - Day 15 (prior to dosing)
- Cycle 2
  - Day 1 (prior to dosing)
- Odd numbered cycles thereafter

- Day 1 (prior to dosing)
- EOT
- 1M FUP

Note: Whole blood (~ 5 mL) to be collected in serum acquisition tubes at each of the indicated timepoints.

### 7.3.2 Exploratory Pharmacokinetic Assessment (Specialty Laboratory)

**As of Amendment 5:** Exploratory PK assessments have been omitted. Exploratory PK assessments were initially planned as follows:

*(To support determination of the  $AUC_{inf}$ ,  $AUC_{0-168h}$ ,  $t_{1/2}$ ,  $CL$ ,  $CL_{ss}$ ,  $V_d$ ,  $C_{trough}$  (SOI) and  $C_{max}$  (EOI) concentrations for Sym004, futuximab and modotuximab for exploratory purposes. Data will also enable population PK modeling for further PK characterization; serum to be isolated)*

*(No additional samples will be collected without formal amendment to this protocol. If a collected serum sample is inadequate or insufficient for PK analysis, the analysis may be done using serum from an ADA sample from the same timepoint, if available)*

*(If no infusion is planned on a sampling day, the “SOI” sample should be taken during the visit. The exact time point of PK sampling should be noted in the CRF. In case no dosing is planned for C2D22, the samples for the PK profile at EOI and 6 hours after EOI, D23, and D25 should be skipped.)*

*(In case of crossover from futuximab or modotuximab to Sym004 before EOC2, sampling should continue according to the schedule outlined.)*

- Cycle 1
  - Day 1
    - SOI
    - EOI
    - 6 hours after EOI
  - Day 2 (24 hours after EOI)
  - Day 4 ( $\pm$  24 hours)
  - Day 8 (prior to dosing and at the EOI)
  - Day 15 (prior to dosing and at the EOI)
  - Day 22 (prior to dosing and at the EOI)
- Cycle 2
  - Day 1 (prior to dosing and at the EOI)
  - Day 22
    - SOI
    - EOI
    - 6 hours after EOI
  - Day 23 (24 hours after EOI)
  - Day 25 ( $\pm$  24 hours)
  - Day 29 (EOC2 or equivalent to C3D1 SOI for patients continuing on Sym004)
- Cycles thereafter (patients continuing on or crossing over to Sym004)

- Day 1 (prior to dosing and at the EOI)
- Day 15 (prior to dosing and at the EOI)
- EOT
- 1M FUP

Note: Whole blood (~ 5 mL) to be collected in serum acquisition tubes at each of the indicated timepoints.

### 7.3.3 Genomic Analysis in Peripheral Blood (Specialty Laboratory)

**As of Amendment 5:** Genomic assessments have been omitted with the exception of prescreening genomic sampling for eligibility assessment (\*). Genomic assessments were initially planned as follows:

*(To be performed at prescreening for eligibility determination; within 28 days prior to first dose of IMP; may be extended to allow for receipt of genomic analysis results. Peripheral blood to be collected)*

- Prescreening (for eligibility)\*
- EOC2
  - Day 25 ( $\pm$  24 hours) *(coincides with PK sampling and pharmacodynamic sampling for all patients and “prior to crossover” for patients in Arm B and Arm C)*
- EOT with Sym004 *(need not be repeated if patient is discontinuing at the EOC2)*
- At the time of radiographically confirmed PD if different from the above

Note: Whole blood ( $\sim 2 \times 10$  mL) to be collected at each timepoint (plus additional  $\sim 2 \times 10$  mL at prescreening to be stored for assay validation purposes); for assessment of ctDNA by *Guardant360*; where blood sample is to be drawn on the day of biopsy (skin; tumor if performed), blood collection to occur prior to performing biopsy procedure(s)

### 7.3.4 Pharmacodynamic Analyses (Specialty Laboratory)

**As of Amendment 5:** Pharmacodynamic assessments (including collection of peripheral blood, skin biopsies, and tumor biopsies) have been omitted. Pharmacodynamic assessments were initially planned as follows:

*(To be performed after eligibility has been confirmed)*

The purpose of pharmacodynamic assessments is to develop an approach for the identification and validation of biomarkers that may predict which patients are likely to respond to Sym004, and that may change with the possible development of acquired resistance.

Analysis may include biomarkers that are unknown or have not been included in the scientific hypotheses of this trial, but that, during the collection of data from this trial, may emerge as indicators related to Sym004 safety, efficacy, or mechanism of action.

All analyses will be related to and used only in connection with the data collected in the present trial and the development of Sym004. The identity of the patient will remain confidential. The analyses will not have any medical consequences for the patient or their relatives.

Residuals from samples collected will be stored for up to 15 years after completion of the trial, where after all samples will be destroyed.

### 7.3.4.1 Peripheral Blood

*(Samples will be assessed for serum proteins and other potential biomarkers)*

- Screening (after confirmation of eligibility)\*
- EOC2\*\*
  - Day 25 ( $\pm$  24 hours) *(preferred day of sampling; coincides with PK sampling and genomic analysis for all patients and “prior to crossover” for patients in Arm B and Arm C)*
- EOT with Sym004 (need not be repeated if patient is discontinuing at the EOC2)
- At the time of radiographically confirmed PD if different from the above

*\*Screening sampling may be conducted at any time prior to CID1, including on CID1 prior to dosing.*

*\*\*End of Cycle sampling may be conducted at any time during the week prior to Day 1 of the next cycle, including on Day 1 of the next cycle, prior to dosing.*

Note: Whole blood ( $\sim 1 \times 20$  mL) to be collected at each timepoint; where blood sample is to be drawn on the day of biopsy (skin; tumor if performed), blood collection to occur prior to performing biopsy procedure(s).

### 7.3.4.2 Skin Biopsies

*(Biopsy specimens to be obtained using standard techniques and formalin-fixed, paraffin-embedded according to standard laboratory techniques. Skin biopsies are requested from a rash-free area)*

*(Samples will be assessed for various parameters, which may include but are not limited to EGFR expression and downstream signaling, markers(s) of proliferation, genomic alterations, etc.)*

- Screening (after confirmation of eligibility)\*
- EOC1\*\*
- EOC2\*\*
  - Day 25 ( $\pm$  24 hours) *(preferred day of sampling; coincides with PK sampling and genomic analysis for all patients and “prior to crossover” for patients in Arm B and Arm C)*

*\*Screening sampling may be conducted at any time prior to CID1, including on CID1 prior to dosing.*

*\*\*End of Cycle sampling may be conducted at any time during the week prior to Day 1 of the next cycle, including on Day 1 of the next cycle, prior to dosing.*

Note: Procedure to be performed after collecting blood sample for pharmacodynamic analyses.

### 7.3.4.3 Tumor Biopsies

*(Samples will be assessed for various parameters, which may include but are not limited to EGFR expression and downstream signaling, markers(s) of proliferation, genomic alterations, etc.) Tissue obtained will be cultured in vitro in order to derive primary tumor and non-tumor cell lines. Selected tumor tissue will also be used for engraftment in immuno-compromised mice. Once the tumor is established, it will be expanded by engrafting in multiple mouse*

recipients, followed by cryopreservation to be used for subsequent biomarker, genotyping, and preclinical drug evaluation studies by the Sponsor.

- Screening (after confirmation of eligibility)\*
- EOC2\*\*
  - Day 25 ( $\pm$  24 hours) (preferred day of sampling; coincides with PK sampling and genomic analysis for all patients and “prior to crossover” for patients in Arm B and Arm C)

\*Screening sampling may be conducted at any time prior to CID1, including on CID1 prior to dosing.

\*\*End of Cycle sampling may be conducted at any time during the week prior to Day 1 of the next cycle, including on Day 1 of the next cycle, prior to dosing.

Note: Tumor tissue for fresh/frozen cells to be collected at each timepoint; procedure to be performed after collecting blood samples for genomic and pharmacodynamic analyses.

Tumor biopsies to include core samples (if feasible, 3 at screening, 2 at EOC2) of a locally recurrent or metastatic lesion; to be performed with minimal morbidity to the patient by a percutaneous core needle biopsy either with or without the aid of an imaging modality chosen at the discretion of the physician performing the biopsy.

Biopsy specimens will be obtained using standard sterile surgical techniques and handled as directed. A detailed laboratory manual specifying sample collection, handling, storage, and shipment will be provided to the trial sites.

## 7.4 Disease Assessments

### 7.4.1 Diagnostic Imaging for Tumor Measurements (Local Assessment)

*(Imaging studies may be used to document tumor status at screening if performed within 14 days prior to first dose of IMP)*

*To include diagnostic imaging by CT or MRI of the chest, abdomen and pelvis, and other sites as indicated based on suspected tumor location and clinical judgment to assess the status of the underlying malignancy. Use of contrast is preferred but is at the discretion of the Investigator, as medically indicated.*

*The same method(s) of disease evaluation and the same technique should be used throughout the study. Additional imaging (such as bone scan) must be performed when other areas of disease are suspected.*

*For all imaging timepoints, the following will be recorded as per RECIST v1.1: target lesions including size, location, and type (nodal/non-nodal); sum of diameters of target lesions; non-target lesions including size, location, and type; any new lesions noted during trial, including size, location, and type (nodal/non-nodal).*

- Screening
- **As of Amendment 5:** frequency per either institutional guidelines or Investigator discretion until confirmation of PD

Patients receiving Sym004 with confirmed PD will be discontinued from further treatment so that alternative management of their malignancy may be considered. Patients receiving

futuximab or modotuximab with confirmed PD will be offered the opportunity to crossover to receive Sym004 or will be discontinued from further treatment so that alternative management of their malignancy may be considered.

Once PD is documented and treatment is discontinued and/or another therapeutic intervention is initiated, no further disease assessments will be required.

***Imaging data (imaging studies and derived assessments) will be stored according to usual practice by the sites and will be available upon request for potential review by the Sponsor or an independent radiology reviewer.***

#### **7.4.2 Response Assessment (Local Assessment)**

*(To be assessed by the Investigator or qualified designee as per RECIST v1.1; to be noted at each evaluation point as CR, PR, SD, PD, or Not Evaluable [NE] for patient management purposes and to make decisions on continued study treatment)*

- **As of Amendment 5:** frequency per either institutional guidelines or Investigator discretion until confirmation of PD

Standard response criteria will be applied (RECIST v1.1, [Appendix 5](#)).

## 8 MANAGEMENT OF TOXICITY

Comprehensive assessments of any toxicity experienced by the patient will be performed throughout the course of this study. The Principal Investigator, Sub-Investigator, or designated health professional must be available throughout the course of the study to evaluate and treat any AE(s), as well as to evaluate whether continued participation in the trial is warranted or advisable.

If, at any point during the study, significant changes occur in either the patient's clinical status or laboratory assessments, such changes will be followed until the abnormality either resolves, returns to baseline status, or is adequately explained.

Anticipated toxicities that may be experienced with IMPs are detailed in this protocol (**Section 2.5, Section 11**), as well as in the IB. Patients will be evaluated throughout the course of the trial for evidence of acute as well as delayed and/or cumulative toxicities.

If a significant toxicity thought to be related to IMP is experienced at any point during the patient's participation in the study, the Investigator will determine appropriate management, including determining whether that toxicity is such that a change in premedication or a dose modification option such as infusion prolongation, temporary dose delay or dose reduction is warranted. Toxicities where management requires discontinuation from study treatment are detailed in **Section 9.1**.

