### 9.1 Criteria for Treatment Discontinuation

Patients will be discontinued from further treatment with IMP in the event of any of the following:

1. Progressive Disease: Confirmed radiographically (and evaluated according to RECIST v1.1)

*Note: Patients receiving futuximab or modotuximab with documented PD at the EOC2 (or prior to the EOC2) will be offered the opportunity to crossover to receive Sym004 or will be discontinued from study.*

2. Clinical Progression: Treatment failure not meeting the criteria for PD, but considered by the Investigator to require treatment discontinuation (i.e., global deterioration characterized by worsening PS, weight loss, and/or worsening clinical symptoms). **Every effort will be made to obtain imaging studies at the time of clinical progression.**

3. Adverse Event including:

- Hepatotoxicity characterized by:
  - AST and/or ALT elevation  $> 3 \times$  ULN (or  $> 3 \times$  baseline if elevated at study entry due to hepatic involvement by tumor), with
  - total bilirubin  $\geq 2 \times$  ULN without initial findings of cholestasis (i.e., serum ALP  $< 2 \times$  ULN), and
  - No explanation for the above findings such as viral hepatic injury, preexisting or acute liver disease, or another drug or condition capable of causing the observed injury

*Adapted from: Hy's Law. Drug-induced liver injury: premarketing clinical evaluation. Guidance for Industry. U.S. Department of HHS, FDA, CDER, CBER, 2009*

- Any of the following AEs:
  - Need for more than 2 dose reductions (Arm A), or more than 1 dose reduction (Arm B or Arm C)
  - Grade 4 IRR
  - Grade 4 EGFR-associated dermatologic AE
  - Torsade de pointes arrhythmia or other life-threatening arrhythmias
- Any other AE or SAE considered by the Investigator to require treatment discontinuation

Note: AEs resulting in a patient's permanent discontinuation from study treatment, regardless of seriousness or relationship to IMP, MUST be reported promptly to the Sponsor (or designee).

In the event of Grade 3 treatment-related AEs that are self-limiting or manageable by supportive care or other therapy, the patient may continue in study if there is evidence of response, disease stabilization, or other clinical benefit, but must do so at a reduced dose of IMP (see **Section 8.2.3**). Patients may not be retreated until retreatment criteria are met (see **Section 6.7.1**).

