**C. Dose Reduction Guidelines for IMP-Related Dermatologic AEs**

Dose delay and/or inpatient dose-reduction(s) will be required upon occurrence of Grade 3 anti-EGFR-associated dermatologic AE, and should be implemented according to the following tables (**Table 24**, **Table 25**):

Table 24: Dose Reduction for Grade 3 Dermatologic AEs - Sym004			
Dermatologic AE Grade 3	Immediate Action	Outcome Improvement	Sym004
First occurrence	Delay dose	Grade ≤1	Continue at same dose
		Grade 2	Reduce to 4.5 mg/kg
		No improvement	Discontinue
Second occurrence	Delay dose	Grade ≤1	Continue at same dose
		Grade 2	At dose of 6.0 mg/kg: Reduce to 4.5 mg/kg At dose of 4.5 mg/kg: Reduce to 3.0 mg
		No improvement	Discontinue
Third occurrence	Delay dose	Grade ≤1	Continue at same dose
		Grade 2	At dose of 6.0 mg/kg: Reduce to 4.5 mg/kg At dose of 4.5 mg/kg: Reduce to 3.0 mg/kg At dose of 3.0 mg/kg: Discontinue
		No improvement	Discontinue
Fourth occurrence	Discontinue	Any	Discontinue

Abbreviations (in alphabetical order): kg, kilogram; mg, milligram

Note: Dose reductions for 9 mg/kg loading NA. For dose delays, re-assess after ≤ 2 weeks. Longer delays are allowed if no recovery to < Grade 2 after 2 weeks

Table 25: Dose Reduction for Grade 3 Dermatologic AEs - Futuximab or Modotuximab			
Dermatologic AE Grade 3	Immediate Action	Outcome Improvement	Futuximab or Modotuximab
First occurrence	Delay dose	Grade ≤1	Continue at same dose
		Grade 2	Reduce to 1.5 mg/kg
		No improvement	Discontinue
Second occurrence	Delay dose	Grade ≤1	Continue at same dose
		Grade 2	At dose of 3.0 mg/kg: Reduce to 1.5 mg/kg At dose of 1.5 mg/kg: Discontinue
		No improvement	Discontinue

Abbreviations (in alphabetical order): kg, kilogram; mg, milligram

Note: Dose reductions for 9 mg/kg loading NA. For dose delays, re-assess after ≤ 2 weeks. Longer delays are allowed if no recovery to < Grade 2 after 2 weeks

In each case, the next treatment should be delayed, and the patient’s condition should be re-assessed after 1-2 weeks. Treatment should be delayed further if the AE remains at Grade 3 after 2 weeks.

In the case of a Grade 2 dermatologic AE which is locally debilitating for the patient, the guidelines outlined above may be followed at the Investigator’s discretion.

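### For repeated Grade 3 skin events on Sym004, Sections 8.2.3 and 9.1 and Table 24 of Appendix 7 give different dose and stopping rules

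*Protocol*

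**What the plan says.** **Pointer.** Section 8 says: "Toxicities where management requires discontinuation from study treatment are detailed in" Section 9.1.

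**Stops in 9.1.** The adverse-event stops that bear on skin toxicity are "Grade 4 EGFR-associated dermatologic AE" and "Need for more than 2 dose reductions (Arm A), or more than 1 dose reduction (Arm B or Arm C". There is also a discretionary item, "Any other AE or SAE considered by the Investigator to require treatment discontinuation". Nothing counts repeated Grade 3 skin events. The synopsis discontinuation criteria and Section 11.3 contain no such count either.

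**Dose rule in the body.** For a Grade 3 related event that is self-limiting or manageable, 9.1 says "the patient may continue in study if there is evidence of response, disease stabilization, or other clinical benefit". It then attaches a condition on dose to that permission: "but must do so at a reduced dose of IMP". Section 8.2.3 and the synopsis text on dose reduction say the same. Table 6 allows two steps for Sym004: 6 to 4.5 to 3 mg/kg.

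**Appendix 7, part C.** Dose delay and/or reduction "will be required upon occurrence of Grade 3 anti-EGFR-associated dermatologic AE, and should be implemented according to the following tables". In Table 24 (Sym004), recovery to Grade 1 or less after the first, second or third Grade 3 skin event means the dose is kept. Recovery to Grade 2 means one step down, or a stop if the patient is already at 3 mg/kg. No improvement means a stop. The row "Fourth occurrence" ends treatment for any outcome. Table 25 (futuximab or modotuximab) has the same layout but ends at the second event.

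**The concern.** A site that follows Section 8 to 9.1 finds one rule for dose and stopping after Grade 3 skin events. A site that opens Appendix 7 finds another. The two disagree on the dose after the first event that recovers well, and on the event at which treatment must end. The mandatory stop by event count appears only in an appendix table, although Section 8 names 9.1 as the place where such stops are detailed.

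At stake are whether and at what dose a patient is treated again, and when an adverse-event discontinuation is recorded. Prompt reporting of such a discontinuation is required under 9.1 and 12.1 whichever section triggers it. What differs is whether and when it occurs. Section 2.6 names skin toxicity among the most frequent Grade 3 or higher events on the 9/6 mg/kg regimen, and Amendment 5 withdrew neither 9.1 nor Appendix 7.

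**Working it through.** The plan gives no figure to reproduce, so the check follows each text consistently for one patient on Sym004 6 mg/kg.

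Inputs: the reduction steps and limit of two (Table 6; 9.1, Arm A); the obligation to reduce (8.2.3, 9.1); the outcome rows of Table 24. Every event is taken to be manageable, with evidence of benefit and the retreatment criteria of 6.7.1 met, because 9.1 allows continuation only then. Every event recovers to Grade 1 or less.

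| Grade 3 skin event | 8.2.3 and 9.1 | Table 24 |
|---|---|---|
| 1 | 6 to 4.5 mg/kg | stays at 6 mg/kg |
| 2 | 4.5 to 3 mg/kg | stays at 6 mg/kg |
| 3 | a third reduction would be needed; 3 > 2, so stop | stays at 6 mg/kg |
| 4 | not reached | stop |

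Next, let each of the first three events recover either to Grade 1 or less or to Grade 2, leaving aside the no-improvement rows. That gives 2 × 2 × 2 = 8 patterns.

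- Under 8.2.3 and 9.1, recovery grade does not change the obligation to reduce, so all 8 stop at event 3.
- Under Table 24, 1 pattern (Grade 2 each time) stops at event 3 and 7 reach event 4. At that point 1 is at 6 mg/kg, 3 are at 4.5 mg/kg and 3 are at 3 mg/kg (1 + 3 + 3 = 7). All 7 then stop.

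The two texts therefore agree on the stopping event in 1 of 8 patterns and differ by one event in 7 of 8. These are counts of patterns, not probabilities.

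Frequency cannot be derived from the documents. For illustration only, take Table 1's 24.1% as the share of patients with acneiform rash of Grade 3 or higher, and assume a 20% to 50% chance of recurrence after each event (an assumption; no source in the protocol). The share reaching a fourth event is then 0.241 × 0.2³ = 0.002 to 0.241 × 0.5³ = 0.030, that is 0.2% to 3.0%. Table 1's caption can also be read as a share of reactions. Then 0.576 × 0.241 = 0.139, and the range is about 0.1% to 1.7%. For two patients, the larger range gives 2 × 0.002 = 0.004 to 2 × 0.030 = 0.06 expected. The dose disagreement does not need repeated events: it arises at the first Grade 3 skin event that recovers to Grade 1 or less.

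**The case against.** **The 9.1 list is not exhaustive.** It is introduced as inclusive and ends with an investigator-judgement item. This stands in part: stopping at a fourth event breaches nothing in 9.1. But judgement is not a mandatory count, and the item does not settle the dose conflict.

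**The specific appendix governs.** Sections 6.5.4.8, 8.1.2 and 11.3 and the note to Table 6 all send sites to Appendix 7, whose required action is delay and/or reduction. Section 8.2.2.2 also lets dosing resume unchanged after a delay. This is a reasonable way to read the protocol, but the protocol does not say so. Sections 8.2.3 and 9.1 make no exception for skin events, and Section 8 names 9.1 for the stops.

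**A stronger reading is tempting.** A reader might infer that 9.1 lets a patient continue on a reduced dose at the fourth event, exactly where Table 24 ends treatment. In 4 of the 7 patterns that reach event 4, two or fewer reductions would then have been used, counting the one at event 4. The documents do not support this. It applies Table 24 to events 1 to 3 and switches to 9.1 at event 4. Followed from the start, 9.1 has already stopped the patient at event 3.

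**The trial is closing.** Accrual is halted and two patients have been treated. That limits the size, but Section 6.7.3 lets both continue Sym004 until progression is confirmed, and safety is all that is still evaluated.

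**Conclusion.** The contradiction holds for Grade 3 skin events on Sym004. The body text requires a lower dose at each event and, by its limit of two reductions, a stop at the third. Table 24 can keep the dose through three events and requires a stop at the fourth. The fourth-event stop is absent from 9.1 and the synopsis despite Section 8's pointer, and so are the no-improvement stops of Tables 24 and 25.

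This rests on the wording alone, with the conditions for continuing under 9.1 taken as met. The number of patients affected is expected to be very small. The 0.2% to 3.0% illustration depends on assumed recurrence rates and should carry no weight. Table 25's silence after the second event has little current effect, since both patients have been crossed over or enrolled to Sym004. The review takes no view on which rule is clinically right.

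**What to change.** Reconcile Sections 8, 8.2.3 and 9.1, the synopsis criteria and Appendix 7 (Tables 24 and 25), so that one dose and stopping rule for repeated Grade 3 skin events applies throughout, or state which text takes precedence. Section 8.2.2.2 should be checked in the same pass. The sponsor must decide which rule holds:

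- If Appendix 7 is to govern skin events, 8.2.3, 9.1 and the synopsis need to say so and to carry its stops.
- If 8.2.3 and 9.1 are to govern, the same-dose and fourth-event entries of the tables need to match them.

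In either case, Table 25 should state what applies after the second event. Adding the fourth-event stop to 9.1, or deleting that row from Table 24, would not be enough, because the same-dose versus reduced-dose conflict would remain.

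The cost is a few sentences and table entries, made by formal amendment as Section 13.4.1 requires. No data collection or analysis changes.
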